## **2.2 Study Objectives**

### **2.2.1 Primary**

- Evaluate the effect of multiple intravenous (IV) doses of GMI-1070 at two different dose levels on time to resolution of vaso-occlusive crisis (VOC) in subjects 12 to 60 years of age hospitalized for sickle cell VOC

### **2.2.2 Secondary**

- Evaluate the effect of multiple IV doses of GMI-1070 at two different dose levels on clinical activity in subjects 12 to 60 years of age hospitalized for sickle cell VOC

- Evaluate the safety of multiple IV doses of GMI-1070 at two different dose levels in subjects 12 to 60 years of age hospitalized for sickle cell VOC
- Evaluate the pharmacokinetics (PK) of multiple IV doses of GMI-1070 at two different dose levels in subjects 12 to 60 years of age hospitalized for sickle cell VOC
- Evaluate biomarkers of adhesion and inflammation at two different dose levels in subjects 12 to 60 years of age hospitalized for sickle cell VOC

### 3 STUDY DESIGN

This is a randomized, double-blind, placebo-controlled trial of multiple IV doses of GMI-1070 or placebo in subjects hospitalized for sickle cell VOC. Investigators are encouraged to identify subjects with VOC who are likely to be admitted, and approach them for consent and eligibility criteria early in the process of treatment for VOC. All subjects should be dosed with study drug within 24 hours of first medical evaluation in the Emergency Department/clinic.

In addition, investigators are encouraged to identify those subjects who may be appropriate for the study before they develop VOC. These subjects may be approached with educational information about the study. Such education will not replace the need to obtain informed consent at the time of hospitalization for VOC.

The study will enroll until approximately 76 evaluable subjects (defined as those who have received at least 1 dose of study medication) have been enrolled. During Visit 1, eligible subjects will be randomized in a 1:1 ratio to either GMI-1070 or placebo using an IVRS. Study drug will be administered as a loading dose of 40 mg/kg followed by 20 mg/kg every  $12 \pm 2$  hours until the subject meets criteria for improvement of pain, or up to 7 days of treatment (maximum 15 doses including the loading dose), whichever comes first. If the subject has no improvement in VOC after 5 days (eg, no change in VAS and no decrease in IV pain medication requirement), study drug should be discontinued.

Resolution of VOC is defined as the first of the following to occur:

- Sustained decrease in pain score of at least 1.5 cm out of 10 cm since baseline; AND transition to oral pain medications per hospital procedures (subject is on no IV pain medications),
- OR readiness for discharge as stated by the physician and subject,
- OR discharge to home.

For the purposes of this study, ‘sustained’ is defined as 2 consecutive pain scores at least 4 hours apart as reported by the subject on a VAS; ‘baseline’ is defined as the pain score just prior to the first dose of study drug as reported by the subject on the VAS.

Visits for follow-up examinations will be made  $36 \pm 12$  hours post last dose (Visit 2) (ideally this will occur prior to discharge from the hospital), on day  $7 \pm 3$  post last dose (Visit 3), and on day  $28 \pm 5$  post last dose (Visit 4).

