**Table 1. Schedule of Assessments**

Visit	Visit 1: During Hospitalization 				Post Last Dose		
	Pre-dose Baseline	IV dosing Every 12±2 Hours up to Day 7			Visit 2	Visit 3	Visit 4
		Loading Dose	At Least q4 Hours (while awake)	Daily Assessments	36±12 hrs	7±3 Days	28±5 Days (or early withdrawal)
Informed consent 	✓						
Inclusion/exclusion criteria	✓						
Randomization 	✓						
Demographics	✓						
Medical history	✓						
Physical examination	✓ 			✓ 	✓ 	✓ 	✓ 
Height, weight	✓ 					✓ 	
Vital signs 	✓			✓	✓	✓	✓
Clinical laboratories 	✓			✓	✓	✓	✓
Urinalysis	✓			✓ 	✓	✓	✓
Pregnancy test (serum or urine)	✓					✓	✓
VAS pain scale	✓		✓		✓	✓	✓
AEs	✓	✓	✓	✓	✓	✓	✓
Concomitant medication	✓	✓	✓	✓	✓	✓	✓

 All subjects should be dosed with study drug within 24 hours of presentation to the Emergency Department/clinic at the latest. Dosing will continue q12 hours until drug is discontinued, for a maximum of 15 doses including the loading dose. Assessments will continue until subject is discharged from the hospital or Day 28, whichever comes first.

 Subjects who remain hospitalized after Day 7 will undergo Visit 1 assessments on each additional day of hospitalization up to Day 28, with VAS scores daily instead of q4 hours on Days 13 to 28. Visits 2, 3, 4 should be completed at the assigned times whether the subject is discharged from the hospital or remains hospitalized.

 Informed consent (and assent, where applicable) must be obtained from all subjects.

 All eligibility criteria must be met prior to randomization.

 Full physical examination.

 Targeted physical examination.

 May be performed within 7 days prior to baseline.

 Weight only.

 Vital signs should be done prior to loading dose, and post-dose for all doses. Oxygen levels may be included as appropriate.

 Complete blood count with differential, platelets, reticulocyte count, high sensitivity C-reactive protein, ALT, AST, bilirubin (fractionated), blood urea nitrogen, creatinine, electrolytes with glucose, LDH. Hb electrophoresis sample to be collected at Pre-dose Baseline only; where possible may be performed on CBC sample. Results of this test are not required for study entry.

 Performed every other day.

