### 5.1.3 Discontinuation of Study Drug

Subjects will be treated with study drug until they meet the following criteria for resolution of VOC:

- Sustained decrease in pain score of at least 1.5 cm out of 10 cm since baseline; AND transition to oral pain medications per hospital procedures (subject is on no IV pain meds)
- OR readiness for discharge as stated by the physician and subject
- OR discharge to home

For the purposes of this study, ‘sustained’ is defined as 2 consecutive pain scores at least 4 hours apart as reported by the subject on a VAS; ‘baseline’ is defined as the pain score just prior to the first dose of study drug as reported by the subject on the VAS.

Study drug should be discontinued if any of the following medical changes take place, and study evaluations should continue to be performed as outlined in Table 1:

- Subject is transferred to ICU for any medical reason

- Acute chest syndrome is diagnosed
- Acute stroke, or other acute CNS changes
- Fever >39° C (102.2° F); fever with negative chest radiograph does not require discontinuation of study drug unless determined to be medically appropriate by the investigator
- Elevated WBC >35,000/mm^3
- No improvement in VOC (as determined by the investigator, based on VAS and opioid or pain medication requirements and the judgment of the investigator) after 5 days of study drug
- Unexpected rise in creatinine, consistent with acute renal failure
- Pregnancy

Note: If it has been determined that study medication should be stopped no weaning of study medication will take place.

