### **6.1.3 Visit 1**

Visit 1 is considered to be the period of hospitalization, during which subjects will be dosed and samples will be obtained for PK assessments and, where applicable, biomarkers and IVM.

All subjects should be dosed with study drug within 24 hours of initial medical evaluation in the Emergency Department/clinic at the latest. Dosing will continue q12 hours until study drug is discontinued. The weight measured at Baseline will be used to determine the appropriate dose administered throughout the study. Study drug will be administered as described in Section 5.1.2.

Results of all assessments, particularly AEs and VAS scores, should be reviewed by the investigator or qualified designee on a daily basis after dosing with study drug is initiated. At a minimum, this review will be documented by the reviewers dated initials.

The calendar date and 24-hour clock time of the beginning and end of each infusion will be recorded in the medical record and on the CRF.

PK sampling will commence as described in Section 6.4. Biomarker and IVM sampling will commence at selected sites. AE and concomitant medication information will be collected during this period.

Subjects who remain hospitalized after Day 7 will undergo the following assessments for each additional day of hospitalization up to Day 28:

- Days 8 to 12: Same assessments expected for Days 1 to 7 (Visit 1).
- Days 13 to 28: Same assessments expected for Days 1 to 7 (Visit 1) with VAS scores collected daily instead of q4 hours.
- Visits 2, 3, 4 should be completed at the assigned times whether the subject is discharged from the hospital or remains hospitalized.

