**6.2 Efficacy Evaluation**

Resolution of VOC will be assessed via a 10 cm VAS scale (to be provided with the CRF), IV opioid and IV NSAID use, readiness for hospital discharge, and time of actual hospital discharge.

VAS data will be recorded a minimum of every 4 hours (while awake) throughout the inpatient study period. Subject pain cards will be provided for use at each pain assessment. The subject will be asked a general question, such as, "how is your pain now?" and the subject will record the answer on a continuous pain scale. The card will be placed in the source record.

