#### **8.2.3.1 Primary Efficacy Analysis**

The primary efficacy endpoint is the time to resolution of VOC from the time the subject receives his or her first dose. Resolution of VOC is defined as the first of the following to occur:

- Sustained decrease in pain score of at least 1.5 cm out of 10 cm since baseline; AND transition to oral pain medications per hospital procedures (subject is on no IV pain medications),
- OR readiness for discharge as stated by the physician and subject,
- OR discharge to home.

The null hypothesis of no difference in time to resolution of VOC between active and placebo treatment groups will be evaluated by using the F-test from an

analysis of covariance (ANCOVA) model, controlling for sex, age and Hemoglobin A level. No censoring is anticipated as the time to discharge will be known for all subjects. Inferential testing will be performed using a fixed-sequence testing procedure.

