### **8.3.2 Sample Size**

Evaluable subjects are those who have received at least 1 dose of study medication. Subjects in the evaluable population will be used to determine when an adequate sample size has been achieved.

The study will enroll until a total of approximately 76 evaluable subjects (defined as those who have received at least 1 dose of study medication) have been enrolled. An interim analysis will be done after the first 50 subjects have completed the follow-up day 7 post last dose, to assess safety and efficacy. The efficacy test statistic for this interim analysis will be compared to a critical value corresponding to a 2-sided alpha of 0.005. To control study wise Type I error, an alpha spending approach will be utilized. The final analysis will then compare the test statistic to a critical value corresponding to 2-sided alpha of 0.045. Futility criteria will also be considered; these will be specified in detail in the statistical analysis plan.

A previous pilot study of treatments for pain in SCD showed the mean pain duration in placebo group is 103 hours with a standard deviation of 60 hours. The original protocol sample sizing was done as follows. Assuming that the variances are the same in both groups and anticipating that the study drug will decrease pain duration by 40%, a total of at least 76 subjects (38 subjects each group) will be needed to detect a 40% decrease in VOC resolution and to achieve 83% power with a 2-sided alpha of 0.045.

With the addition of a second dose level, the power calculation for the study has been updated to compare the treatment difference between the placebo group and the pooled active group (ie, both dose levels combined). The sample sizing assumes that the placebo group has a mean pain duration of 103 hours with a standard deviation of 60 hours, and that both groups – placebo and pooled active groups – share a common standard deviation. Anticipating that the placebo and pooled active groups will each have about 38 subjects (ie, the pooled group will have 19 subjects from each of the dose levels) the study will have an 89% power to detect a 43.8% decrease in VOC duration with a 2-sided alpha of 0.045.

The sample size is also expected to provide initial safety and PK conclusions sufficient to contribute to the design of subsequent trials.

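### The definition of a sustained pain decrease sets a minimum gap of 4 hours between consecutive scores, while the schedule sets a maximum waking gap of 4 hours, so the timing of this endpoint component depends on how often a site scores

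*Protocol*

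**What the plan says.** Resolution of VOC is the first of three events. The pain-score route in Section 8.2.3.1 is "Sustained decrease in pain score of at least 1.5 cm out of 10 cm since baseline; AND transition to oral pain medications per hospital procedures", with no IV pain medication remaining. The alternatives are "OR readiness for discharge as stated by the physician and subject" and discharge home.

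The synopsis, Section 3 and Section 5.1.3 define sustained as "2 consecutive pain scores at least 4 hours apart as reported by the subject on a VAS". Section 8.2.3.1 uses the word without defining it.

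On assessment, Section 6.2 states: "VAS data will be recorded a minimum of every 4 hours (while awake) throughout the inpatient study period". Table 1 gives the same frequency. For subjects still in hospital on Days 13 to 28, Section 6.1.3 has "VAS scores collected daily instead of q4 hours".

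The definition also has a bedside use. Section 5.1.3 says: "Subjects will be treated with study drug until they meet the following criteria for resolution of VOC".

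**The concern.** One rule sets a floor of 4 hours on the gap between consecutive scores. The other sets a ceiling of 4 hours on the same gap while the subject is awake. Read literally, they meet at a single point. More frequent scoring is allowed, and it makes the criterion harder to satisfy: closer observation of a subject who is already better postpones the recorded event.

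At stake is the timing of the one component of the primary endpoint that uses a VAS score. If sites differ in scoring habits, or in how they read the sentence, the same course of pain gives different resolution times. The text does not say how scores taken between two qualifying scores count.

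**Working it through.** **Inputs from the protocol.** Minimum gap for a qualifying pair: 4 h (synopsis, Sections 3 and 5.1.3). Maximum waking gap: 4 h (Section 6.2, Table 1). Section 8.3.2 assumes that "the mean pain duration in placebo group is 103 hours with a standard deviation of 60 hours", with 38 per group and two-sided alpha 0.045.

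**The plan's own figures.** A 40% decrease is 0.40 × 103 = 41.2 h; 43.8% is 45.1 h. The standard error is 60 × √(2/38) = 13.76 h. With a noncentral t on 74 df, power is 82.8% and 89.0%, which reproduces the stated 83% and 89%. The point below does not alter these.

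**Interval logic.** A waking pair needs gap ≥ 4 h to qualify and gap ≤ 4 h to comply, so gap = 4 h exactly. Longer compliant gaps arise only during sleep, or with daily scores on Days 13 to 28.

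**Example.** Take a subject off IV analgesia whose scores are all below threshold from 08:00.
- Scored at 08:00 and 12:00: qualifies at 12:00, after 4 h.
- Scored at 08:00, 11:00, 14:00, 17:00, 20:00, 23:00 and 07:00: every waking gap is 3 h. The first qualifying pair is 23:00 to 07:00, so confirmation comes after 23 h. A rule requiring all scores over a span of at least 4 h is met at 14:00, after 6 h.

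**Size of the delay.** The following are assumptions, not from the protocol: 16 h awake and 8 h asleep, relief starting at a random time and lasting, no other resolution route applied, and the event timed at the confirming score under both rules. The delay is mean time to confirmation under the written rule minus that under the span rule.

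| Scoring pattern | Waking gaps ≥ 4 h | Written rule (h) | Span rule (h) | Delay (h) |
|---|---|---|---|---|
| Exactly every 4 h | 100% | 7.3 | 7.3 | 0 |
| Every 4 h, timing SD 10–20 min | about 50% | 10.1–10.3 | 9.4–9.5 | 0.7 |
| Every 4 h, never late | 0% | 20.69 | 11.44 | 9.25 |
| Every 3 h | 0% | 21.02 | 9.77 | 11.25 |
| Every 2 h | 0% | 20.09 | 6.80 | 13.29 |

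In the last three rows every first qualifying pair falls overnight. With intervals drawn at random, the mean delay is 10.4 h for 3–4 h scoring and 12.6 h for 2–3 h scoring.

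**Sensitivity to the order of events.** Those delays assume that pain relief and the end of IV analgesia coincide. If relief comes first, an overnight pair may already exist when IV treatment stops. For the same 2–3 h and 3–4 h patterns, the mean delay is about 9 h with a 12 h lead, about 2 h (median 0) with a 24 h lead, and 0 with a 36 h lead.

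**Effect on power.** Treat the delay as independent noise with SD 8 h. The total SD is √(60² + 8²) = 60.5 h, and power for 41.2 h moves from 82.8% to about 82.2%.

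**The case against.** The strongest reply is that the protocol's natural schedule is one score every 4 hours; Section 6.1.3 and a footnote to Table 1 call it simply that. A site scoring at exactly 4 hours complies and satisfies the definition with every pair. With ordinary timing error about half of the waking pairs still qualify, although gaps over 4 hours then breach the schedule, and the mean delay is under an hour. A reader might infer that a compliant site almost never meets the rule except overnight. The documents do not support that. It holds only for sites that score more often than every 4 hours or are never late.

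Second, nothing requires both scores to follow the end of IV analgesia, and Section 5.2.1 suggests weaning once pain is controlled. A lead of a day or more is plausible against an assumed mean of 103 hours, and it removes most of the delay. This stands, but the lead time is an assumption either way.

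Third, the other routes limit the effect. Section 6.5.5 asks the readiness question alongside pain scores once IV opioids are being weaned, and Section 5.2.1 mentions as little as 6 hours on oral medication as a discharge criterion. This also stands; the share of subjects resolving by each route is not given.

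Fourth, one might set 10 hours against the 41.2-hour difference and infer that a quarter of the treatment effect is lost. That does not follow. The delay is largely common to both arms, and randomization is stratified by site (Section 5.1.4).

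None of this removes the conflict in the text or its silence on intermediate scores.

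**Conclusion.** The definition and the schedule conflict as written. For subjects scored more often than every 4 hours, the timing of the pain-score component depends on scoring frequency and sleep as well as on pain. The delay ranges from nil at exact 4-hourly scoring to about 10 to 13 hours when scoring is more frequent and relief coincides with the end of IV analgesia. Its size in this trial cannot be fixed from the protocol, because it turns on site scoring habits, the order of pain relief and IV withdrawal, and how often readiness or discharge comes first. The consequence is avoidable site-dependent noise in a primary-endpoint component. It is neither a demonstrated bias between arms nor a material loss of power. It is worth correcting because the repair is small and the wording is also used at the bedside.

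**What to change.** In Section 8.2.3.1, define sustained for the endpoint analysis: all VAS scores, at least two, over a span of at least 4 hours from first to last, are 1.5 cm or more below baseline. Scores within the span then count towards the criterion and do not break the pair. Any pair that meets the present wording also meets this one, since no score lies between consecutive scores, so no subject resolves later under it. Whether the event is timed at the first or last score of the span is a separate choice and is not part of this point.

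The synopsis, Section 3 and Section 5.1.3 carry the same wording and also determine when study drug stops. They, together with Section 6.2 and Table 1, must be reconciled with the endpoint text; what the bedside rule should be is for the sponsor and its clinical advisers.

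The cost is a sentence in Section 8.2.3.1 and a consistency edit in the other places. No new data are needed, since inpatient VAS scores are already collected at these intervals.

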### ***Pharmacokinetics Sampling***

Plasma sampling for PK will be done during the study. A total of 9 samples will be drawn from each subject. Each sample will be 3 mL. Urine sampling for PK will also take place, in a single 12-hour urine collection.

### ***Optional Site-specific Biomarkers***

In a subset of subjects at sites capable of performing these tests, IVM testing for microvascular blood flow and additional sampling for other biomarkers of adhesion and inflammation will be performed.

## **4 SELECTION AND WITHDRAWAL OF SUBJECTS**

### **4.1 Number of Subjects**

The study plans to enroll until approximately 76 evaluable subjects (defined as those who have received at least 1 dose of study medication) have been enrolled.

### **4.2 Inclusion Criteria**

To be eligible for inclusion, each subject must fulfill each of the following criteria at screening, and must continue to fulfill these criteria prior to dosing:

1. 12 to 60 years of age
2. Confirmed diagnosis of sickle cell disease (HbSS or HbS- $\beta^0$ thalassemia)
3. Diagnosis of VOC at the time of enrollment
4. Hospitalized or in process of admission at the time of enrollment
5. Able to receive the first dose of study drug within 24 hours of initial medical evaluation in the Emergency Department/clinic for VOC;
  - Subjects treated as an outpatient within the past 48 hours for the same VOC episode may be enrolled if dosing is also expected within 24 hours of their second (admitting) presentation.
6. Documented and observed written informed consent (and assent, where applicable)

### **4.3 Exclusion Criteria**

1. Infection, diagnosed or strongly suspected, as evidenced by 1 or more of the following:
  - Fever  $>39^\circ\text{C}$  ( $102.2^\circ\text{F}$ )
  - In the presence of fever  $\geq 38.5^\circ\text{C}$  ( $101.3^\circ\text{F}$ ), 1 of the following:

- 
- Positive findings (suspicious for infection) on diagnostic tests, such as CSF evaluation, radiographs, or bacterial culture of normally sterile sites
  - Exam findings leading to diagnosed or strongly suspected bone or joint infection
  - Determination by physician that bacterial or serious systemic viral infection is likely (eg, influenza, mononucleosis)
  - Subjects may be included with uncomplicated urinary tract infections (provided they do not have fever  $\geq 38.5^{\circ}\text{C}$  [ $101.3^{\circ}\text{F}$ ] or CVA tenderness), and/or suspected minor viral syndromes (upper respiratory infection symptoms but no symptoms suggestive of bacterial infection other than uncomplicated otitis media or, uncomplicated streptococcal pharyngitis)
2. Acute chest syndrome, diagnosed or strongly suspected, as evidenced by a new infiltrate on chest radiograph, and 1 or more of the following:
    - Fever  $>39^{\circ}\text{C}$  ( $102.2^{\circ}\text{F}$ )
    - Hypoxia (confirmed by arterial blood gases [ABG] with  $\text{paO}_2 < 70\text{ mmHg}$ )
    - Chest pain
    - Suspicious findings on exam (tachypnea, intercostal retractions, wheezing, and/or rales)
  3. SCD pain atypical of VOC, including hepatic or splenic sequestration, cholecystitis, or pneumonia.
  4. Acute stroke, acute priapism, severe avascular necrosis of the hip/shoulder when the presenting pain is only in the affected hip/shoulder
  5. Serum creatinine:
    - $>1.2\text{ mg/dL}$  for subjects 16 to 60 years of age
    - $>1.0\text{ mg/dL}$  for subjects 12 to 15 years of age
  6. Alanine transaminase (ALT/SGPT)  $>2\text{x ULN}$  (based on clinic laboratory normal range)
  7. Hemoglobin  $<5\text{ g/dL}$
  8. Platelets  $<100,000/\text{mm}^3$
  9. Recent (within the past 30 days) major surgery, hospitalization for other than VOC, documented serious bacterial infection requiring antibiotic treatment, or significant bleeding
  10. Hospitalization for uncomplicated VOC, or treated with parenteral pain medications in other medical settings such as the emergency department or day hospital for uncomplicated VOC, within past 14 days;
    - Subjects may be included if treated as an outpatient within the past 48 hours for the same VOC episode
  11. Recent (within the past 90 days) cerebrovascular accident, transient ischemic attack, or seizure
  12. pRBC transfusions in the past 14 days
  13. Systemic steroid therapy within 48 hours prior to enrollment or expectation that therapy may be used during the study (inhaled or topical steroids are allowed)
  14. For those on chronic or long-acting opioids, a change in dose in the past 14 days OR pain requiring medical attention in the past 14 days (change in opioid medication for acute pain in the past 48 hours and directly related to this VOC admission is allowed)

15. Greater than 5 episodes of hospitalization for VOC in the past 6 months (180 days)
16. Medical or psychiatric condition that, in the opinion of the investigator, may pose a risk to the subject for participation or interfere with the conduct or results of the study
17. Currently receiving, or has received within the previous 4 weeks, any other investigational agent
18. Previous administration of GMI-1070
19. Expectation that the subject will not be able to be followed for the duration of the study
20. Pregnant or lactating female; or female of childbearing potential or male unable or unwilling to comply with birth control methods or abstinence during the course of the study
21. Active use of illicit drugs and/or alcohol dependence, as determined by the investigator

